Strategies to minimize risk: Risks to subjects are minimal and may include loss of confidentiality and psychological discomfort about discussing issues related to their neuropsychological assessment. Prior to enrollment, the study will be explained in a clear and detailed manner by the study coordinator (serving in role as coordinator and psychometrist) and investigators. All participants will be reminded at the beginning of all assessments of their right to terminate the assessment at any time. In the study consent procedure and study activities, we will clearly state that all participants can refuse to answer any questions or to review any of the study materials. Research staff will be trained to address psychological distress and will follow standard procedures for referral for mental health evaluation. We will also reassure patients that if they choose not to be in the study, it will not affect the medical care they normally receive.

We will provide neuropsychological test results from the FF condition (i.e., condition that is most congruent with standard of care) to the referring neurologist and the patient, and this information will also be placed in a research note in their UCH EMR. This will be explicitly noted in consent form and reviewed in detail with the participant. In terms of study results, there is a possibility of practice effects, particularly on memory tests and fluency tests, with serial testing. Studies suggest minimal practice effects in individuals with symptomatic Alzheimer's disease; however, given that we will provide results from the FF assessment to be used in clinical care and potentially for diagnosis, we will mitigate risk in the following way: a) use of alternate forms, where possible and b) require of at least one month between conditions. Based on these strategies, which are also used in standard of care with neuropsychological serial testing, we do not think enrollment in the study poses a significant risk of a clinically meaningful practice effect.

Strategies to manage and protect the privacy of participants and confidentiality of research data: A copy of the consent form will be given to each participant. Maintenance of subject confidentiality is a high priority for the proposed research project. Video-based TeleNP will be conducted using

HIPAA-compliant platform supported by UC Health and CU Anschutz Medical Campus. Video assessments will not be recorded. All written and audio-recorded data (i.e., stakeholder semi-structured interviews) and consent materials will be given anonymous identification numbers and will be stored on a password protected private database on computers in locked offices. The consent forms and the key for identification of subject names corresponding to identification numbers will be stored in a separate locked file cabinet. For audio-recorded data (i.e., semi-structured interviews), research assistants will redact any spoken identifiers (names, etc.) from transcripts and will label audio-files with a sequential de-identified number. Study data will be collected and managed using REDCap (Research Electronic Data Capture). Only key study personnel will have access to these data. REDCap is a secure web application designed to support data capture for research studies, providing user-friendly web-based case report forms, real-time data entry validation (e.g. for data types and range checks), audit trails, and a de-identified data export mechanism to common statistical packages (SPSS, SAS, Stata, R/S-Plus).

Plans for ensuring professional intervention if indicated: Participants will be given the PI's contact information for any questions or concerns about the study. Staff will be trained to identify and address psychological distress, reportable events, or threats to society including elder abuse, suicide or homicide ideation or intent, violent behavior or threats, excessive emotional outbursts, a witnessed psychotic break with visual or auditory hallucinations, verbalization of anxiety or flashbacks to past traumatic experiences, and reports of major depression (assessed in the study). For acute issues, hospital security will be called [contact]). For nonacute issues, the research team will be available in clinic to help avert crises and to schedule potential needed follow-up. If elder abuse is suspected, we will contact the patient's Colorado county law enforcement agency and county-specific adult protective services intake phone number through standard reporting mechanisms. The informed consent forms state that if elder abuse is suspected it will be reported, in accordance with State of Colorado law. A toll free crisis line will be made available to participants who may be in abusive situations ([name]), and the referring neurologist will be alerted to suspected elder abuse.

Plans for handling incidental findings: Participants will receive results from their FF research assessment. Through the process of completing the study procedures, the most likely potential incidental findings will be new or worsened physical or psychological distress, or delirium. If the intervention is stopped due to discomfort and/or the patient desires for the research staff to share information about their current needs with the patient's UCH Memory Disorders Clinic neurologist, the psychometrist will communicate this information on the patient's behalf. Of note, if information emerges during either the TeleNP or FF visit that requires immediate clinical action, or clearly would impact treatment, the neuropsychologist will immediately notify the participant and neurologist to streamline care and minimize any delays in treatment. Moreover, if any safety, psychological or other signs of distress related to potential diagnosis of AD are noted during either assessment, appropriate referrals will be coordinated by Drs. [name] and [name].

To improve reach to participants who have limited access to technology and conduct TeleNP using a standardized technology platform, we will provide a 4G tablet to all participants via a research lending library. Participants will be encouraged to bring a care partner, if available, with them to visits (i.e., FF and TeleNP); however, consistent with standard clinical practice, the availability of a care partner will not be a requirement.

E. Potential Scientific Problems:

Practice Effects: Repeated administration of cognitive tests is sometimes associated with practice effects, which may impact interpretation of results. Practice effects have been shown to be lower in symptomatic (MCI, dementia) patients relative to asymptomatic adults³⁴; with respect to individual domains, verbal memory tests and verbally-mediated executive function measures appear to be most vulnerable to practice effects, with visuospatial measures less impacted. In estimating practice effects over a 3- to 6-month period, maximum effect sizes have ranged from 0.10 to 0.15 based on drug trials, which are quite small.³⁴ Our proposed period (4-6 weeks) occurs over a shorter duration. Based on recommendations for clinical trials³⁴, we will use alternate forms, where available (i.e., memory tests; fluency measures; attention/working memory). Of note, we will provide feedback to the patient and referring neurologist based on the FF assessment. In cases where the participant undergoes the FF assessment *after* the TeleNP condition, it is possible that aforementioned practice effects, albeit very small, may influence the mean scores obtained for each cognitive domain. Serial testing is common in standard neuropsychological practice, thus we will use validated approaches (i.e., alternate forms) for tests that are most vulnerable to this effect.

Diagnosis: While neuropsychologists will be apprised of the study design, they will be blinded to the *specific* referral diagnosis (i.e., typical vs atypical AD); moreover, the neuropsychologist will be asked to provide *their own determination* and given the option of including “Not AD” as their provisional diagnosis. The goal of this approach is to minimize bias and circularity; however, it remains possible that neuropsychologist-specific effects will be present (i.e., tendency to rate participants as “complex”). We will assess in exploratory analyses whether there were provider-specific effects on outcomes. We acknowledge that the division of diagnoses into three categories (i.e., subjective concerns; MCI; dementia) does not fully map onto NIA-AA diagnostic criteria for MCI² and AD dementia¹; however, most neuropsychologists do not have access to fluid/PET biomarkers in clinical practice, thus our approach more pragmatically represents standard of care. Nonetheless, neuropsychologists often do provide specific diagnoses for complex phenotypes, including focal presentations (e.g., posterior cortical atrophy). As an exploratory strategy, we will consider providing an additional diagnostic field for the neuropsychologist to indicate specific considerations in their differential.

Statistical Analysis Framework: We are evaluating equivalence by examining mean Z-scores per cognitive domain, aggregated across multiple tests; however, individual tests have different test-retest reliabilities, which are often evaluated on a patient-specific level through the use of reliable change indices (RCIs). Given the pilot nature of this clinical trial, it is possible that a .5SD difference in mean domain score will not accurately reflect a clinically meaningful difference in individual test scores. As such, we will consider examining test-specific differences across modalities using published test-rest reliability.

Technological Difficulties: We have incorporated several approaches to minimize and troubleshoot technological difficulties, including a pre-visit test call, inclusion of care partner in the process, and provision of a study tablet to all participants. Consistent with Aim 3, **we will track technological issues throughout the study procedures to inform changes that might be beneficial to a larger clinical trial**. In addition, we will include a discussion during monthly team meetings regarding any technological issues that arise.

F. Statistical Analysis Plan:

For **Aim 1**, we will adopt an equivalence testing framework. The null hypothesis is that there is an average difference of at least .5 SD units in the difference in the z-scores, where .5 SD defines a potentially clinically meaningful difference. The alternative hypothesis is that the mean of the

difference in the z-scores is zero. This is the reverse of standard statistical testing. We elected a .5 SD margin as an initial threshold for a clinically meaningful difference; the reason for this decision is that once an individual reaches a level deemed to be clinically significant impairment (e.g., mild impairment = -1.5 SD; moderate impairment =-2.0 SD), a change in .5 SD equates to a categorical difference in their overall severity rating. To conduct our equivalence test, we will compute the difference in the z-score between the FF and TeleNP conditions and compute the mean difference and a 90% confidence interval based on a t-test. This results in an equivalence test with an alpha=0.05. If the entirety of bounds of the 90% confidence interval are between (-.5SD, .5SD), then the two assessments will be considered equivalent. We will repeat this computation stratified by referring diagnosis (typical vs. atypical), and also by sex or race/ethnicity (white vs. non-White).

For **Aim 2**, we will compute a 3x3 table with the rows as TeleNP diagnosis and the columns as FF diagnosis to summarize the results. To assess the equivalence of TeleNP and FF for each condition we will create 3, 2x2 tables. For example, when assessing for differences in typical AD we will collapse over atypical AD and Not AD. Following prior work³⁵, we will compute the difference proportion of typical AD for the TeleNP and FF setting and construct a 90% confidence interval. A difference of proportions greater than 5% will be considered a clinically meaningful difference. If the 90% confidence interval is between (-5%,5%), then the two modalities will be considered equivalent. We will repeat this process for the two other neuropsychologist-determined categories (atypical AD, Not AD). We will conduct the same analyses, stratified by severity. We will assess whether the neuropsychologists' diagnosis is equivalent to the Flexible Assessment by repeating the above analysis using the Flexible vs FF diagnosis (i.e., diagnosis reported prior to initiating Flexible Assessment).

For Aim 3, Feasibility and Acceptability of Intervention Measures and the UTAUT will be analyzed descriptively with means and interquartile ranges. Analysis of qualitative data will be a continuous process beginning with initial interviews and continuing throughout the data generation period. All interviews will be audio-recorded and transcribed verbatim. Directed by [name], rapid qualitative analysis³⁶ will be used to understand multiple user perspectives on feasibility, acceptability, and other potential factors affecting use, including home context, of TeleNP compared to FF. At least 2 team members will analyze transcripts.³⁷ All data will be entered into ATLAS.ti v8.0 (GmbH, Berlin) for data management. Transcripts will be analyzed to develop the major themes or concepts reported by interviewees. Using the quantitative and qualitative data, we will conduct sequential mixed methods analyses using data from Aim 3.³⁸ The synthesis stage of data analysis involves triangulating the findings from interviews and quantitative data related to feasibility (i.e., assessment time, protocol adherence, technical issues, etc.), acceptability ratings, availability of a care partner, etc. We will interpret and summarize feasibility and acceptability for each modality from the different user perspective

G. Summarize Knowledge to be Gained:

Appraisal of the feasibility and validity of TeleNP in patients with complex AD presentations will provide a critical platform for the future development of a pragmatic, multi-site trial. Validation of TeleNP in a real-world setting will further increase access to neuropsychological evaluations and reduce patient burden. Specific knowledge to be gained includes:

- Comparison of two testing modalities for neuropsychology: telehealth and standard, face-to-face assessment
- Comparison of diagnostic adjudication for these two neuropsychology modalities
- Test- and interview-specific differences in feasibility and validity in these two modalities

- Qualitative information regarding feasibility, participant experience and acceptability, care partner experience and acceptability, and psychometrist & neuropsychologist experience.
- Greater understanding of technological concerns that may arise in telehealth
- Preliminary understanding of potential benefits of telehealth, both qualitatively and quantitatively

H. References:

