The overarching goal of this proposal is to a) assess the feasibility and preliminary validity of **home-based delivery of TeleNP** to patients with suspected AD, referred for cognitive assessments in a Neurology Clinic; and b) elucidate whether TeleNP is equivalent to face-to-face evaluation (FF) for diagnostic adjudication of atypical versus typical AD. To accomplish these goals, we will conduct a **pilot clinical trial** of two testing modalities, TeleNP versus FF, for delivery of neuropsychological evaluations. Neurologist-referred patients with typical (i.e., memory-predominant; n=40) and atypical (i.e., complex and/or non-memory predominant; n=40) presentations of *possible* AD will be enrolled in the study. Care partners of participants will also be consented to the study and included in stakeholder surveys/interviews. Using a cross-over design, all participants will undergo evaluations (clinical interview + Core Battery of cognitive tests) in both modalities, approximately 4-6 weeks apart to account for potential practice effects. Although all participants will be referred due to suspected AD, the neuropsychologist will be blinded to the specific diagnosis (i.e. typical versus atypical) from the neurologist. The Core Battery will include measures of memory, executive, visuospatial, and language functions. To further minimize practice effects, alternate assessment forms will be implemented and order of test forms will be counterbalanced. Some tests are not readily adaptable to video-based delivery due to tactile/physical stimuli; as such, we will assess whether a Flexible Assessment (i.e., option to include additional tests, after completion of Core Battery) in the FF modality alters diagnostic conclusions. Finally, in an exploratory aim, we will identify stakeholder perspectives of TeleNP that inform pragmatic implementation of remote neuropsychological evaluations. Our Aims are:

Aim 1: Determine the validity of home-based video administration of neuropsychological tests (TeleNP) for assessing AD. 1a: Are cognitive test results equivalent across TeleNP and FF conditions in patients with suspected AD? 1b. Is this equivalence consistent across referral diagnoses (i.e., Typical vs. Atypical AD)? *This Aim will test the validity of cognitive measures assessed with TeleNP and determine whether the validity of TeleNP differs based on referral diagnosis.*

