Protocol and Core Battery (2 hours): In both conditions (FF; TeleNP), **the neuropsychologist will first conduct a structured, 30-minute interview with the participant and care partner, if available, which is a standard component of neuropsychological assessments.** The psychometrist will subsequently conduct a Core Battery of standardized neuropsychological assessments (see Data Collection below). The majority (60%) of clinical neuropsychologists employ psychometrists to administer their tests, thus our approach simulates clinical practice.²⁴ Tests in the Core Battery were selected based on: a) breadth: coverage of all primary domains (i.e., memory^{25, 26}, attention/executive functions^{27, 28}, visuospatial²⁹, and language functions³⁰); b) use in clinical practice: frequent use in neuropsychological evaluations with established, validated norms in older adult populations; c) availability of alternate forms: presence of alternate forms, where possible, for tests most sensitive to practice effects (e.g., memory, verbally-mediated executive measures); and d) adaptability to TeleNP: inclusion of tests that minimize use of physical/tactile stimuli; i.e., inclusion of tests that may be screen shared via remote video technology and/or permit the patient to utilize their own piece of paper. The psychometrist will score the Core Battery based on published normative data for an older adult population using an automated excel calculator and provide the demographic-adjusted scores to the neuropsychologist. The neuropsychologist will document their diagnosis and severity of the participant's presentation.

Assessment Modality Details:

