--Participants' age, birthdate, sex, gender, education level (Years), race/ethnicity, prior occupation, etc. will be obtained. Participant's contact information and address will also be obtained to facilitate scheduling baseline and follow-up appointments.

Interview:

--Participant's symptom history will be documented on a standard data collection sheet during the interview portion.

Neuropsychological Testing, Core Battery (May not be given in its entirety):

- Cognitive/Mood Surveys:
 - Geriatric Depression Scale
- Cognitive Assessments:
 - Global:
 - MoCA, with alternate forms
 - Memory:
 - CVLT-II, with alternate forms
 - Benson Figure Recall / RBANS Figure Recall
 - Speed/Executive Functions:
 - Oral Trail Making Test
 - Oral Symbol Digit Modality
 - Digit Span, with alternate forms
 - Verbal Fluency, with alternate forms (FAS; BHR)
 - Color Word Inhibition
 - Language:
 - Sentence Repetition
 - Boston Naming Test-15 item, with alternate forms
 - Verbal Agility
 - WRAT Reading
 - Abbreviated Peabody Picture Vocabulary Test
 - Syntactic Comprehension
 - Visuospatial and Posterior Cortical Function
 - Judgment of Line Orientation (Short Form)
 - Benson Figure Copy / RBANS Figure Copy
 - Calculation Screen

Neuropsychological Testing, Flexible Assessment:

- Cognitive Assessments in addition to Core Battery (May not be administered in its entirety):
 - Grooved Pegboard
 - Clock Drawing Test
 - Rey-Osterrieth Complex Figure
 - BVMT
 - Navon Figures
 - Face Perception/Affect Naming
 - VOSP Number Localization
 - Design Fluency
 - Written Trail Making Test A & B

Surveys:

- 4-item measures of acceptability and feasibility
- 19-item modified UTAUT after TeleNP portion

Cognitive Composites, Neuropsychologist Diagnosis, and Interviews: See Outcome Measures Below

Data Collection for Care Partner Participants:

Demographics:

--Care partner's age, birthdate, sex, gender, education level (Years), race/ethnicity, prior occupation, etc. will be obtained. Participant's contact information and address will also be obtained to facilitate scheduling baseline and follow-up appointments.

Surveys:

- 4-item measures of acceptability and feasibility
- 19-item modified UTAUT after TeleNP portion

Interviews: See Outcome Measures Below

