Incorporation of Results into Clinical Care: Because the set battery used in the FF assessment uses validated tests that are normally used for these patients in clinical care, it is likely that patients in this study *will not* undergo a separate standard of care neuropsychological assessment. Therefore, a brief research overview of the results of the FF assessment will be provided to the referring neurologist and the participant after both conditions are complete (and posted to Epic Medical Record as a research note), for use in their clinical care. Based on a

national survey, the median time between neuropsychological assessment and completion of reports is 3 weeks; our proposed time is slightly longer than the median, but remains within an expected range for clinical reports.³¹ Of note, when considering the amount of time between referral and scheduled date of assessment in SOC (often on the order of months), our window will likely be shorter/faster than SOC given dedicate research time. If any safety, psychological or other signs of distress related to potential diagnosis of AD are noted during either assessment, appropriate referrals will be coordinated by Drs. [name] and [name]. Drs. [name] and [name] will coordinate with the neurologist to determine if prompt discussion of the first assessment is clinically prudent. The research note posted to Epic EMR will include a brief background/history, table of scores for FF condition, and summary/recommendations, consistent with standard of care approaches.

C. Outcome Measure(s):

Aim 1: Equivalence of Cognitive Test Results: *The goal of this Aim is to test the concurrent validity of cognitive measures across testing modalities and determine whether the test results differ based on referral diagnosis.* Z-scores will be calculated based on age-referenced normative data for each cognitive test (Table 1) in the Core Battery. For data reduction purposes, a mean z-score for each cognitive domain will be used (i.e., memory, executive functions, spatial abilities, language). This will allow us to address whether neuropsychological test results are equivalent across modality (i.e., FF vs. TeleNP) and whether complexity of referral impacts comparability of test results.

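### The Aim 1 interval ignores which test form was used in which modality, so any gap between forms widens it and can shift a stratum by chance; a form term is a cheap, optional improvement

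*Combined protocol and SAP*

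**What the plan says.** - **Design.** Section I (Specific Aims) states that "alternate assessment forms will be implemented and order of test forms will be counterbalanced". Section IV.B randomises the order of modality in REDCap and names no stratification factor. Neither section says whether form order is crossed with modality order or balanced within subgroups.
- **Which tests.** The Core Battery criteria in IV.B ask for "presence of alternate forms, where possible, for tests most sensitive to practice effects". The test list marks the MoCA, CVLT-II, Digit Span, Verbal Fluency and 15-item Boston Naming Test this way, for example "CVLT-II, with alternate forms". The figure tasks appear differently, as "Benson Figure Recall / RBANS Figure Recall" and "Benson Figure Copy / RBANS Figure Copy", without that label.
- **Outcome.** Under Outcome Measures, Aim 1, "Z-scores will be calculated based on age-referenced normative data for each cognitive test", and then "a mean z-score for each cognitive domain will be used". Form-specific norms and equating are not mentioned.
- **Analysis.** Under F. Statistical Analysis Plan, Aim 1, "we will compute the difference in the z-score between the FF and TeleNP conditions and compute the mean difference and a 90% confidence interval". Equivalence is declared if the interval lies within ±0.5 SD. The calculation is repeated by referral diagnosis, sex and race/ethnicity.

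**The concern.** When the form changes between visits, a patient's FF minus TeleNP difference is also a difference between two forms. With balanced counterbalancing the form gap enters as plus for half the patients and minus for the other half. It drops out of the mean but stays in the SD, and the one-sample t interval treats it as random noise although the design fixes it. The interval is then wider than the design needs.

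The plan also repeats the interval in subgroups where form balance is left to chance. In a particular stratum the gap need not cancel, and part of it would be read as a modality difference. This matters most for Aim 1b, which rests on two groups of 40, and for the sex and race/ethnicity strata, which could be smaller.

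**Working it through.** **The plan's own figure.** A 90% interval gives (1 − 0.90)/2 = 0.05 per one-sided test, which matches the stated alpha. The plan gives no SD of differences, power or form gap for Aim 1.

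**Inputs from the documents.** n = 80 overall, 40 per referral group, margin 0.5, 90% interval.

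**Assumptions.** SD of differences within form assignment 0.75. Two memory tests are averaged, and only one of them has a form gap of d, so the gap on the domain mean is f = d/2. The range shown is d = 0.25 to 1.0 z.

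**Model.** D = δ + s·f + e, where s = +1 or −1 records which form was used in FF.

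**1. Width under balance.** SD = √(0.75² + f²·n/(n − 1)) and half-width = t(0.95, n − 1)·SD/√n.

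| d | f | n=40 | n=80 |
|---|---|---|---|
| 0 | 0 | 0.200 | 0.140 |
| 0.25 | 0.125 | 0.203 | 0.142 |
| 0.5 | 0.25 | 0.211 | 0.147 |
| 1.0 | 0.5 | 0.241 | 0.168 |

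For example, at n=40 and d=1.0, SD = √(0.5625 + 0.25 × 40/39) = 0.905 and the half-width is 1.685 × 0.905/6.325 = 0.241.

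**2. Chance of declaring equivalence** (simulation; plain t interval against a model with a term for the form used in FF).

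- n=40, true difference 0: 98.4% against about 98.8% (d=0.5); 96.9% against about 98.8% (d=1.0).
- n=40, true difference 0.2: 77% against 80% (d=0.5); 69% against 80% (d=1.0). At d=0.25 the loss is under one percentage point.
- n=80, true difference 0: essentially 100% either way for every d.
- n=80, true difference 0.3, d=1.0: about 65% against 76%.

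**3. Strata.** If k of n patients have one form assignment, the estimate shifts by f·(2k/n − 1). For a 25:15 split of 40 that is 0.25·f, or 0.05 to 0.075 for f = 0.2 to 0.3. With SD 0.7 and f = 0.2 to 0.3, simulated type I error at the margin is 0.036 to 0.049 averaged over allocations. Given an unfavourable split it is 0.10 to 0.13 (15:25 of 40) or 0.11 to 0.15 (4:11 of an assumed stratum of 15). Given a favourable 10:5 split it falls to 0.01 to 0.02. With the form term it is 0.047 to 0.051.

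**4. Which term to add.** The sign of the gap in FF minus TeleNP is form order multiplied by modality order. In a balanced 2×2 crossing (n=40, d=1.0, true difference 0.2), a term for form order alone leaves the pass rate at 69%, and a term for the form used in FF raises it to 80%. The coding also matters. In an assumed stratum of 12 with random form assignment and d=1.0, one-sided error at the margin is about 0.05 with the plain interval and with fixed +1/−1 coding. It rises to about 0.08 if the indicator is re-centred within the stratum, because the intercept then returns to the raw mean while the interval narrows.

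**The case against.** The strongest reply is that nothing here endangers the main result. Extra width is conservative, the plan's alternative is a zero mean difference, and at zero the n=80 test passes regardless. Norm-based z-scores may already remove much of any gap, averaging dilutes what remains, and the trial is a pilot. All of this stands.

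Three stronger readings are tempting, and the documents do not support them.

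- **That the figure instrument changes between visits.** This would be inferred from a slash. The pair lacks the alternate-forms label given to other tests, and it could equally mean a choice or that both are given. Table 1, cited under Outcome Measures, is not in the text available for this review and may settle it.
- **That the strata are biased.** Chance imbalance in form has mean zero, and its variance is already in the t interval's SD. The shift exists only conditionally on an uneven split. Failing an equivalence test is also not evidence of a modality effect.
- **That form is confounded with modality.** If form order were tied to modality order, TeleNP could always receive the same form and the whole gap would fall on the contrast. With SD 0.75, n=80 and no true difference, the pass rate would be about 90% at d=0.5 and 5% at d=1.0. The text does not exclude this arrangement, but nothing says it is planned.

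**Conclusion.** The concern holds as a matter of efficiency. The design controls form and the Aim 1 interval does not use it, so a form gap adds width overall and, given an uneven split, moves a stratum estimate. Under the stated assumptions, at n=40 the half-width grows by about 6% for a 0.5 z gap on one test (0.211/0.200) and by about 20% for a 1.0 z gap (0.241/0.200). The effect is negligible at 0.25 z or less. The average error rate stays at about 0.05 or below, and the n=80 conclusion at a true difference of zero is unchanged. The SD, the form gap, the number of tests averaged and the sizes of the strata of 12 and 15 are all assumptions. If the Benson and RBANS figures are alternates, they are the likeliest source of a sizeable gap. This is an optional, low-cost improvement; Aim 1 is not invalid without it.

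**What to change.** 1. Record the form, and the figure instrument, used at each visit. State in IV.B that form order is crossed with modality order, so that neither modality always receives the same form.
2. In the Aim 1 analysis, replace the one-sample t interval with a linear model of the FF minus TeleNP difference on an indicator of which form was used in FF (form order multiplied by modality order). Code it as fixed +1/−1 and do not re-centre it within strata. Use the intercept and its 90% interval overall and in each stratum large enough to fit the model. A single indicator suffices if a patient's forms are assigned as one set.
3. State whether the Benson and RBANS figures are alternates across visits. If they are, report the estimated gap between them.

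**Cost.** One recorded variable, a sentence or two in the plan and one degree of freedom: with no form gap, the n=40 half-width changes by about 0.001 or less. Unbalanced strata pay slightly more. The intercept's standard error is (SD/2)·√(1/k + 1/(n − k)), which is 0.163·SD against 0.158·SD for 15:25 of 40 (3% more) and 0.292·SD against 0.258·SD for 4:11 of 15 (13% more).
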